Robbin et al 2006 (18)	126	
 • Duplex Scan (Ultrasound) 	AVG	AVG Survival	Not beneficial
Tessitore et al. 2004	79	
 • Access flow 	AVF	Thrombosis	Beneficial

Study Design

Randomized, Prospective Clinical Trial. Patients, PI, funder (Transonic) and statistician blinded (this will be implemented in Velos). Intervention and standard of care are different and cannot be blinded from attending nurses or clinic personnel. If a patient needs to switch schedules, they need to switch to shift that matches their protocol. Otherwise, they will need to switch protocols. No Transonic (funding) personnel will be involved in study design, protocol, analysis, or publication.

Randomization:

Patient is consented, baseline assessment taken, and evaluated for inclusion before randomization (baseline data will be included in analysis to determine representativeness of study patients to clinic patients). Randomization will occur after enrollment period ends.

The intervention and control protocols are significantly different that individual patients in the same dialysis session would be able to identify which arm they are in. Therefore, blocks of patients will be randomized according to dialysis schedule within each clinic.

Hemodialysis Access Surveillance Evaluation (HASE) Study

Because the staffing is similar across shifts, we will do block randomization where all patients in a shift are assigned to the same protocol at each clinic site. For each clinic, the blocks will be given a number based on chronological order (Monday 1st shift = 1, Monday 2nd shift = 2 +, Monday 3rd shift = 3, Tuesday 1st shift = 4, Tuesday 2nd shift = 5, Tuesday 3rd shift = 6). For each clinic site, a coin will be flipped in front of two witnesses: heads = first group treatment; tails = first group control. Then a die will be rolled. The number that is rolled will the first group assigned (based on coin toss). The remaining groups will be allocated in sequence. For instance, if the coin lands on heads and the die lands on 3, Monday 3rd shift is intervention, Tuesday 1st shift is control, Tuesday 2nd shift is intervention, Tuesday 3rd shift if control, Monday 1st shift is intervention and Monday 2nd shift is control. If a patient has to switch dialysis schedules, care must be taken to place them in the same arm.

Inclusion and Exclusion Criteria

Inclusion criteria:

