Chronic hemodialysis patients undergoing dialysis therapy via an upper extremity arteriovenous access (arteriovenous fistula or an arteriovenous graft) will be enrolled to have monthly surveillance flow measurement using Transonic system or physical examination of the arteriovenous access by qualified person at least once a month for a period of 2 years.

Exclusion criteria:

- Patients requiring surgical intervention on the arteriovenous access.
- History of access thrombosis (one or more access thrombosis of the current AV access).
- Patients with signs of access infection.
- Patients with a malignancy.
- Patients with life expectancy of less than six months.
- Unable to understand the study.
- Unable to sign the consent form.
- Patients with psychiatric disorder.
- Age less than 18 or greater than 80 years.
- Adults unable to consent
- Individuals who are not yet adults (infants, children, teenagers)
- Pregnant women
- Prisoners

Procedures Involved

Chronic hemodialysis patients receiving treatment with an upper extremity arteriovenous access will be enrolled in this 2 year study. End of study starts as last patient from 450 completes follow-up. Patients would be randomly assigned into surveillance or the control group. Randomization will take a cluster pattern per shift. (shift randomization).

Hemodialysis Access Surveillance Evaluation (HASE) Study

Surveillance group

- a. Surveillance group would receive monthly blood flow surveillance by ultrasound dilution technique (using the Transonic system) plus standard care (see below). Patients would be referred for an intervention based on the current KDOQI recommendations i.e. access flow of less than 600 ml/minute for arteriovenous grafts and less than 500 ml/minute for patients with arteriovenous fistulas or if the access flow is 1000 ml/minute that has decreased by more than 25% over 4 months (1). In addition to the detection of access dysfunction, the time interval between the detection of access dysfunction by the Transonic system and the intervention will also be recorded.

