- b. Patients will be referred for an intervention if clinical indication is met. Clinical indications include prolonged bleeding for more than 30 minutes (cannot be explained by medication), upper extremity edema, difficult cannulation, aspiration of clots during cannulation, aneurysmal formation. Access pressure that prevents normal HD machine operation (such as high venous pressure [>250 mm Hg] on three or more consecutive dialysis treatments, negative arterial pressure [<-250 mm hg] on three or more consecutive dialysis treatments). Any Kt/V that cannot be explained by other factors and high recirculation rate of more than 10% would be checked by Transonic Recirculation/flow test prior to referral (rear event).

Control group

Control group will receive standard monitoring (standard care). Standard monitoring is physical examination by a qualified individual (nurse) at each dialysis encounter. Patients will be referred for an intervention if clinical indication is met. Clinical indications include prolonged bleeding for more than 30 minutes, low Kt/v that cannot be explained by other factors, high venous pressure (>250 mm hg) on three or more consecutive dialysis treatments, negative arterial pressure (<-250 mm hg) on three or more consecutive dialysis treatments, upper extremity edema, difficulty cannulation, aspiration of clots during cannulation, aneurysmal formation and high recirculation of more than 10%.

Enrollment period

Enrollment period is expected to be 3-6 months.

Transonic measurement protocol:

Access recirculation, access flow would be determined using the ultrasound dilution technique (Transonic system).

1. Within 90 min of the beginning of HD session HD03 sensors are clamped HD tubing lines
2. Recirculation, access flow will be performed according to HD03 Manual.
3. Post intervention evaluation is as per each arm follow up unless other follow up deemed necessary by the interventionalist.

Hemodialysis Access Surveillance Evaluation (HASE) Study

Data Management

Primary Hypothesis:

H_0 : Patients screened monthly with Transonic Ultrasound Dilution Technique (UDT) and followed up with proactive intervention (if clinically indicated) will not have a rate of access thrombosis that is different than patients receiving physical examination and reactive intervention (if clinically indicated).

Secondary Hypotheses:

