H_{0-1} : Patients screened monthly with UDT and followed up with proactive intervention (if clinically indicated) will not have a time to thrombosis that is different than patients receiving physical examination and reactive intervention (if clinically indicated)

H_{0-2} : Patients screened monthly with UDT and followed up with proactive intervention (if clinically indicated) will not have a number of angioplasty procedures that is different than patients receiving physical examination and reactive intervention (if clinically indicated)

H_{0-3} : Patients screened monthly with UDT and followed up with proactive intervention (if clinically indicated) will not have a number of thrombectomy procedures that is different than patients receiving physical examination and reactive intervention (if clinically indicated)

H_{0-4} : Patients screened monthly with UDT and followed up with proactive intervention (if clinically indicated) will not have a rate of tunneled dialysis catheter (TDC) that is different than patients receiving physical examination and reactive intervention (if clinically indicated)

H_{0-5} : Patients screened monthly with UDT and followed up with proactive intervention (if clinically indicated) will not have a rate of non-tunneled dialysis catheter (non-TDC) that is different than patients receiving physical examination and reactive intervention (if clinically indicated)

Sample Size:

$\alpha = 0.05$, $\beta = 0.80$, 2-sided (testing benefit and harm)

Main predictor: Treatment or control; Main outcome: Thrombosis or no—two-sided therefore chi-square for proportions of dichotomous variables was used for sample size calculations.

Treatment versus control estimates of thrombosis (based on Tessitore 2004; Scaffaro 2009, Moist 2003, Robbin 2006, Sands 1999, Ram 2003, Tessitore 2008): 34% in control; 24% in treatment (effect size 30%); 342 per group; loss to f/u (move, transplant, different clinic) 5% = $1/(1-.5)=1.05=359$ (low estimate); loss to mortality 10% a year = 1.11 2x (per [name]) = 443

Variables to be collected at baseline:

age, sex, race (white, black, Asian/Pacific Islander, American Indian/Alaskan Native), ethnicity (Hispanic or not), insurance type (private, Medicaid, Medicare,

Hemodialysis Access Surveillance Evaluation (HASE) Study

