Veterans/Military, uninsured), length of time in dialysis (weeks); diabetic (y/d), CAD, PVD, HTN, how long access has been in place (weeks), location (Right/Left, arm/forearm), type of access (AVF or AVG), other clinical variables, button hole, history previous access (Y/N), history of previous catheter (Y/N), length of catheter placement/use (Days)

Variables to be collected monthly:

Monthly questionnaire.

Statistical Analysis:

- **Step 1:** Descriptive analysis to assess similarity of patients between trial arms and to assess representativeness of study participants to hemodialysis patients (generalizability).
- **Step 2:** Descriptive analysis for primary outcome (chi-square) and secondary outcomes (t-test or non-parametric equivalent)
- **Step 3:** Kaplan-Meier Survival Curve (unadjusted)
- **Step 4:** Survival Time Analysis Cox proportional hazards model (adjusted)
- **Step 5:** Multilevel regression with random effects in a mixed regression model to adjust for potential group-level RN, center, city effects. Primary analysis is a dichotomous variable (y/n). Secondary analysis outcomes continuous but may be treated as categorical variables

Covariates for evaluation in the models: individual-level predictors: age, race, sex, insurance, length of time in dialysis (weeks), diabetes (y/n), CVD (y/n), how long access has been in place (weeks), access location, type of access, location of access , length of time in study before thrombosis or mortality (weeks); other significant clinical variables group-level predictors: RN, dialysis center, city

Cross-overs: intervention participants who do not get clinically indicated treatment will be analyzed in two ways--included in treatment arm (intention-to-treat) and excluded (per protocol)

Statistical monitoring: analysis will be conducted 6 months; 12 months; 18 months; and 24 months. If a clear benefit is identified early or if the intervention is unexpectedly harmful, the study will be stopped early.

Risks to Subjects

Risk from Ultrasound Dilution Technique: UDT is a non-invasive procedure that generates no risk to patients undergoing hemodialysis. We do not anticipate any problems as a result of patients undergoing this procedure.

Risk to Privacy: There may be breach of confidentiality regarding protected health information. To minimize the potential risk to privacy all data are de-identified with use of study specific ID numbers only. To ensure that participants' confidentiality is

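### The per-protocol analysis drops patients who miss indicated treatment from the surveillance arm only, and the plan does not say that intention-to-treat decides

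*Combined protocol and SAP*

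**What the plan says.** The cross-overs item under Statistical Analysis contains the only rule on departures from assigned care: "intervention participants who do not get clinically indicated treatment will be analyzed in two ways". The two ways are "included in treatment arm (intention-to-treat) and excluded (per protocol". The words about the treatment arm show that only surveillance patients are meant. The plan ranks neither analysis above the other.

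Both arms have indicated interventions:

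- The primary hypothesis describes surveillance patients as "followed up with proactive intervention (if clinically indicated" and the comparators as "patients receiving physical examination and reactive intervention (if clinically indicated".
- Under Procedures Involved, Control group, controls are referred when an indication is met: "Clinical indications include prolonged bleeding for more than 30 minutes, low Kt/v that cannot be explained by other factors", among others. Most of the same indications apply in the surveillance arm, which also has the access-flow criteria.

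The plan foresees a wait before the procedure, since under Surveillance group "the time interval between the detection of access dysfunction by the Transonic system and the intervention will also be recorded". It sets no maximum wait. It has no rule for an access that clots during the wait.

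**The concern.** A per-protocol set defined by what happens after randomisation always risks losing comparability. Two features make the risk sharper here.

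First, the rule works in one arm. Take two patients with prolonged bleeding, an indication in both arms. Both are referred and neither has the procedure. The control stays in the per-protocol analysis and the surveillance patient leaves it. The flow criteria give surveillance patients further occasions to meet the rule.

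Second, the primary outcome can cause the exclusion. If both accesses clot while waiting, the control counts as a thrombosis. On a literal reading, the surveillance patient did not get the indicated treatment and is removed together with the event. The secondary hypotheses lend this reading some support: they count thrombectomies ("will not have a number of thrombectomy procedures that is different") separately from angioplasties, so a thrombectomy after the clot is not obviously the procedure that had been indicated.

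What is at stake is the per-protocol result and its weight if it disagrees with intention-to-treat, since the plan does not say which one settles the question.

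**Working it through.** **Inputs.** From Sample Size: 34% thrombosis in control and 24% in treatment, two-sided 0.05, chi-square, 342 per group. From Number of Subjects: 450 patients. Assumed: an even split (225 per arm), clustering ignored, and the shares dropped, for which the documents give no figure.

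**The plan's own figure.** The uncorrected two-proportion formula gives

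n0 = [1.96·√(2·0.29·0.71) + 0.8416·√(0.34·0.66 + 0.24·0.76)]² / 0.10² = 322.04, so 323.

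With continuity correction,

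n = (n0/4)·[1 + √(1 + 4/(n0·0.10))]² = 342.

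The stated 342 reproduces with the correction. The point here does not depend on it.

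**Effect of the one-arm exclusion when there is no true effect.** Let p = 0.34 in both arms. Let f be the share of surveillance clotters dropped and g the share of surveillance non-clotters dropped. Then

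- surveillance rate after exclusion: p' = p(1−f) / [p(1−f) + (1−p)(1−g)]
- surveillance patients left: n' = 225·[p(1−f) + (1−p)(1−g)]
- spurious benefit: d = p − p'
- chance of declaring benefit: Φ[(d − 1.96·SE0)/SE1], with SE0 pooled and SE1 unpooled, uncorrected test.

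Worked case, f = 10% and g = 0: p' = 0.306/0.966 = 0.3168, d = 0.0232, n' = 217.3, SE0 = 0.0447, SE1 = 0.0446. Then Φ[(0.0232 − 0.0876)/0.0446] = Φ(−1.44) = 7.5%.

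| Clotters dropped (f) | Non-clotters dropped (g) | p' | Spurious benefit (points) | Benefit declared |
|---|---|---|---|---|
| 0 | 0 | 34.0% | 0 | 2.5% |
| 10% | 0 | 31.7% | 2.3 | 7.5% |
| 10% | 5% | 32.8% | 1.2 | 4.5% |
| 10% | 10% | 34.0% | 0 | 2.5% |
| 10% | 20% | 36.7% | −2.7 | under 2.5% |
| 20% | 0 | 29.2% | 4.8 | about 19% |
| 20% | 10% | 31.4% | 2.6 | 8.1% |
| 20% | 20% | 34.0% | 0 | 2.5% |

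The bias depends on whether clotters or non-clotters are dropped more often. The documents give no basis for choosing a row.

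**How few patients could move a p-value across 0.05.** With control at 76/225, surveillance at 58/225 gives p = 0.064 (uncorrected chi-square). Dropping two patients who clotted gives 56/223 and p = 0.044. With continuity correction that becomes 0.056. Without it, also dropping two non-clotters gives 56/221 and p = 0.051. The example shows sensitivity, not a likely reversal.

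**The case against.** The strongest reply is that intention-to-treat is already planned, stands first in the same sentence, and is untouched; the listed analysis steps mention no exclusion. Only a companion analysis is affected, and a disagreement between the two would be visible. This stands and limits the point. It does not dispose of it, because the plan never says which result prevails.

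The second reply concerns meaning. The rule sits under the label of cross-overs, which suggests a patient who refused or did not attend. A reader might infer that the plan discards every surveillance clot that occurs while a procedure is pending. The plan does not spell that out; it is a literal reading of a rule that leaves missed treatment undefined. On the narrower reading the exclusion is still one-armed, but the outcome need not drive it. If 5% of the arm is dropped, the bias is (0.34 − 0.05r)/0.95 set against 0.34, where r is their thrombosis risk: 0 points at r = 34%, 0.8 in favour of surveillance at r = 50%, and 0.9 against it at r = 17%.

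A reader might also infer that the rule must favour surveillance, or that a couple of exclusions would turn a null trial positive. Neither is supported. The rule also drops non-clotters who miss treatment, which dilutes, cancels or reverses the bias, and the two-patient example fails under the continuity correction that reproduces the plan's 342.

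**Conclusion.** The concern holds for the per-protocol analysis. As written, it applies a post-randomisation exclusion to one arm, although both arms have indicated treatment that can be missed, and it leaves open whether a clot before the procedure triggers the exclusion. The comparison is not like with like.

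Size and direction cannot be fixed from the documents. Under 34% in both arms, 225 per arm and no clustering, the illustrations run from a spurious benefit of 4.8 points (20% of clotters and no non-clotters dropped), through zero when both are dropped equally, to 2.7 points the other way (10% of clotters, 20% of non-clotters). For scale, the planned effect is 10 points.

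The documents do not support a claim that the trial's main conclusion is biased: intention-to-treat is planned and unaffected. The gap is that it is not named as the deciding analysis.

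**What to change.** In the cross-overs item under Statistical Analysis:

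1. State that intention-to-treat is the primary analysis and decides the trial's conclusion.
2. Remove the exclusion that applies to surveillance patients only.
3. If a per-protocol analysis is kept, label it supportive. Apply one rule to both arms, with a treatment window fixed before outcome data are reviewed. Keep patients whose access clots inside the window and count the clot as an event.
4. In that rule, say whether a single qualifying flow is an indication. The Surveillance group text reads that way, but Table 1 in the Background speaks of persistent abnormalities.

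The supportive label is still needed with a common rule, because the flow criteria exist only in the surveillance arm and exclusions may still differ. An adherence-adjusted estimate is optional. It would need its own definition of missed treatment, and it would have to assume that assignment to surveillance does nothing for anyone who misses an indicated procedure.

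The first two changes are wording only and leave referral rules, measurements and sample size alone. The third has a data cost: the plan records the interval from Transonic detection to intervention, so a window in both arms also needs the dates of clinical referrals and of the interventions that follow. The per-protocol result may also look less favourable.

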[name] brings over 20 years' experience to the current study. She has the experience and skills to ensure timely completion of all the project milestones, organize communications among investigators, ensure regulatory and IRB compliance, overs study and effectively multi-task the various administrative duties associated with large complex studies. She also contributes to manuscripts for publication and data presentations at scientific meetings.

- **[name] RN (AMC Study Coordinator and Dialysis Center staff)**

[name] has over 16 years' experience in dialysis access and hemodialysis therapy. She is CITI certified and is highly skilled at recruiting, enrolling and retaining participant's in previous studies. She has demonstrated that she can efficiently and effectively coordinate the flow of participants during their study visits to the CRC, reinforce compliance with study interventions, collect and retain data in a well-organized manner, and maintain updated regulatory documentation and case report forms.

Recruitment Methods

Study staff will identify potential subjects from dialysis centers mentioned above. Subjects will be approached for a brief conversation to establish if there is interest in hearing about the study. If the patient is interested, the study coordinator will then present a detailed explanation of the study.

Subjects who meet all of the inclusion criteria ascertained at the screening visit will be enrolled in the study. In order to reach the goal of 450 subjects who complete the protocol, we will screen up to 900 subjects with CKD, allowing for a screening to enrollment ratio of 2:1. Once the target enrollment is complete we will discontinue screening irrespective of whether we have yet to reach 900 subjects.

Study team members who approach patients at centers will be very careful of explaining to potential subjects that research participation is completely voluntary and that their decision whether to participate or not, will have no impact in their medical care. Also, participants will receive a full explanation of the extent of their participation in the study prior to signing the informed consent form.

Hemodialysis Access Surveillance Evaluation (HASE) Study

Number of Subjects

450 Patients.

Confidentiality

Patients' identifying information will be stored in a password-protected, firewall enabled database, only available to approved study staff. The database will be kept for the duration of the study.

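### Four analyses with early stopping but no boundary: the two-sided 0.05 is not secured, and overall error would be 12–13% if each look used p<0.05

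*Combined protocol and SAP*

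**What the plan says.** The Statistical monitoring paragraph, at the end of Statistical Analysis, says that "analysis will be conducted 6 months; 12 months; 18 months; and 24 months". It goes on: "If a clear benefit is identified early or if the intervention is unexpectedly harmful, the study will be stopped early". These looks can therefore end the trial for efficacy as well as for safety.

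The Sample Size section sets alpha at 0.05, "2-sided (testing benefit and harm", and bases the calculation on a chi-square comparison of thrombosis proportions, 34% against 24%. It arrives at 342 per group and then adds allowances for loss to follow-up and death, ending at 443.

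Statistical Analysis lists several methods. Step 2 is "Descriptive analysis for primary outcome (chi-square) and secondary outcomes". Steps 3 to 5 add Kaplan-Meier curves, an adjusted Cox model and a mixed regression model, and cross-overs are to be analysed both by intention to treat and per protocol. None of these is named as the analysis that decides stopping.

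**The concern.** Each extra look at which the trial can be declared positive adds a chance of a false positive. Unless the interim thresholds are fixed in advance and the final level is lowered to pay for them, the overall error exceeds the nominal level. Here the threshold is left open, so it could be chosen once data have been seen, and so could the test and the analysis set to which it is applied.

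Two things are at stake. The first is the error rate of the primary comparison. The second is the size of the reported effect, because a trial stopped early on a lenient criterion and few events tends to overstate the benefit. The protocol presents this study as the well-powered trial needed to settle a contested question, so an early stop on an inflated estimate would undercut its purpose.

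**Working it through.** **1. The plan's own sample size.** Inputs from Sample Size: 34% and 24% (mean 29%), two-sided 0.05, 80% power.

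- Uncorrected: m = [1.960·√(2·0.29·0.71) + 0.842·√(0.34·0.66 + 0.24·0.76)]² / 0.10² = 322.0
- Continuity-corrected: n = (m/4)·[1 + √(1 + 4/(m·0.10))]² = 341.7, so 342, an exact match.
- Attrition: 342 × 1.05 = 359; 359/0.9² = 443.2 (or 359 × 1.11² = 442.3), against 443 stated.

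This is a fixed single-look formula. The later factors cover only loss to follow-up and death, with no allowance for repeated testing.

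**2. Information at each look.** The Randomization section says "Randomization will occur after enrollment period ends", so patients are taken to start together and looks are counted from that point. Assumptions: constant hazard and pooled thrombosis of 29% at 24 months.

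- Cumulative incidence F(t) = 1 − 0.71^(t/24) = 0.082, 0.157, 0.227, 0.290 at 6, 12, 18 and 24 months.
- Event-based fraction (log-rank or Cox), F(t)/F(24): 0.283, 0.543, 0.781, 1.
- Chi-square on cumulative proportions, where information is proportional to F/(1 − F): 0.219, 0.457, 0.717, 1.

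**3. Overall error.** Under the null, the statistics Z₁ to Z₄ are jointly normal with correlation √(tⱼ/tₖ) for j<k. Overall error = 1 − P(|Zₖ| < cₖ at all four looks), obtained by recursive numerical integration and confirmed by simulation.

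| Interim p (6, 12, 18 months) | Final p | Event-based | Chi-square |
|---|---|---|---|
| 0.05 | 0.05 | 12.3% | 13.0% |
| 0.02 | 0.05 | 7.5% | 7.9% |
| 0.01 | 0.05 | 6.1% | 6.3% |
| 0.005 | 0.05 | 5.5% | 5.6% |
| 0.001 | 0.05 | 5.1% | 5.1% |
| 0.001 | 0.049 | 5.0% | 5.0% |

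In the first row, the benefit direction alone is 6.1% (event-based) or 6.5% (chi-square), and the chance of a false stop before 24 months is 10.5% or 10.9%.

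**4. Sensitivity of the first row to timing.** Equal information gives 12.6%. Adding the plan's attrition to the event-based case gives 12.0%. Counting looks from first entry, with 3 or 6 months of uniform entry, gives 12.8% or 13.3%. Information accruing very late (10/30/60/100%) gives 14.4%, and very early (60/80/90/100%) gives 9.7%.

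**5. Overstated effect.** Recruitment Methods gives a total of 450 patients, so take 225 per arm. Under constant hazards the 6-month risks are 1 − 0.66^0.25 = 9.87% and 1 − 0.76^0.25 = 6.63%.

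- True 6-month relative reduction: 1 − 6.63/9.87 = 33%. The 24-month figure is 10/34 = 29%.
- Expected events: 225 × (0.0987 + 0.0663) = 37.
- In simulation, about 24% of such trials reach p<0.05 for benefit at 6 months, and the median observed reduction among them is 55%. At 342 per arm the median is 48%.

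**The case against.** The plan never says that the looks use p<0.05. Clear benefit, read naturally, suggests something stricter than nominal significance. With interim p<0.001 the inflation is negligible (5.1%), so the 12–13% is the unfavourable end of a range. It also pools both directions; the rate of false benefit is about half of it. The trigger is a matter of judgement, and the protocol blinds the principal investigator, funder and statistician, which limits opportunistic use of the data. Finally, part of the document, between Risks to Subjects and the description of the study team, was not available for this review.

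Much of this is fair as to size, and the 12–13% should be read as conditional. It does not remove the problem, because nothing available commits the trial to a strict threshold. Any interim efficacy stop combined with a final test at 0.05 exceeds 5%, if only slightly. Blinding helps only in part: stopping for benefit requires someone to compare the arms, and the plan does not say who. The monitoring paragraph reads as complete and refers to no charter or boundary elsewhere. Pooling the two directions follows the plan's own two-sided alpha.

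**Conclusion.** The concern holds. The plan's 0.05 is not ensured, and the true overall error cannot be determined from the text. With the final test at 0.05 it runs from about 5.1% (interim p<0.001) to 12.3–13.0% (p<0.05 throughout), or 9.7–14.4% for the latter under extreme information timing. At the lenient end, the chance of a false claim of benefit is more than twice the nominal 2.5%.

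The figures assume a common start, constant hazard, independent patients and the 24-month look as the final analysis. A separate fifth analysis, equally spaced, would raise the p<0.05 case to 14.2%. Randomisation by shift could add further inflation if clustering is ignored.

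This should be settled before any unblinded comparison, because a threshold written after the data are seen cannot restore the error rate.

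**What to change.** Add one paragraph to Statistical monitoring that:

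- names the single test and analysis set that decide stopping, and who carries out the unblinded look;
- fixes the boundary for benefit and for harm, with a separate harm threshold if the sponsor prefers one;
- states the adjusted level for the 24-month test;
- commits to reporting effect estimates adjusted for early stopping.

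Two boundaries would serve; the choice between them is the sponsor's.

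- **Fixed levels:** two-sided p<0.001 at 6, 12 and 18 months and p<0.049 at 24 months. Overall error is 5.0% on both information scales. Power for 34% against 24% falls by about 0.2 points (64.8% to 64.6% at 225 per arm; 82.3% to 82.1% at 342 per arm).
- **Lan-DeMets O'Brien-Fleming spending,** 0.025 per direction: about 0.00005, 0.005, 0.021 and 0.043 at event fractions of 28/54/78/100%. Power falls by about 1 point. The levels must be recomputed from observed information; carried over unchanged to the chi-square scale they give about 5.2%.

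Neither needs more patients. Both hold 5% only if the deciding test also accounts for clustering by shift. That matter, and the mismatch between 450 patients in total and 443 per group, need separate attention.
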